4.1. Overall Design

The study conceptual framework is illustrated in Figure 1. Briefly, we have proposed an observational design. Eligible individuals will be identified during a crisis assessment, either in the emergency department or during an emergency phone or telehealth assessment. Once the individual has been assessed and assigned to the clinician for treatment, study staff will assess if the patient is appropriate for the study using the study eligibility criteria. Individuals who receive treatment in one of the following treatment arms will be eligible for this observation study: inpatient, in-person OCIC or telehealth crisis intervention service. Eligible individuals will be contacted by study staff to introduce and offer the study. If patient and guardian agree, they will complete surveys at baseline and every 2 weeks for 6 months to evaluate outcomes.

Figure 1

Clinical features will be measured with the CHRT-SR, Suicidal Event Form for START, and our short START-Clinical Features (CF) form at baseline and every two weeks (see Schedule of Events) to evaluate HTE's. A one time survey will be completed at week 2 that collects information related to the impact of COVID-19 on the family. To decrease clinician, patient, and family burden, the scales are self-report short forms. All START follow up forms will be sent to participants and guardians every 2 weeks via email prompts in REDCap and data will be collected upon return from participants. Study CRCs will make best efforts to contact families for reminder to complete data within the study milestone window, however completion at each milestone marker is not ensured due to nature of population group. Data will be collected when available. The research coordinators, a research team member, or clinicians will ensure the

completion of the Suicidal Event Form for START and the brief START-CF form based on EHR review and/or other sources of information (family and patients) within 72 hours of admission (baseline) to inpatient, telehealth CIS, or OCIC and every two weeks. The research coordinators will search the EHR for all hospitals (with permission and consent) on weekly basis for suicidal events which may have ICD-10-CM code.¹⁰⁰ We developed this plan based on feedback from patients, families, and clinicians.

The following sociodemographic data will be gathered by our research coordinators or a research team member at baseline (within 72 hours of admission to inpatient, telehealth CIS, or OCIC) with our Demographic Form from our prior and current research on school safety: 1) Age 2) Gender⁵³⁻⁵⁶ 3) Gender Identity⁵⁷⁻⁶⁰ 4) Type of Insurance (public Insurance/no insurance/private)⁶¹⁻⁶³ 5) Ethnicity (Hispanic/Non⁶⁴; 6) Race (African-American (AA) versus non-African American)⁶⁵⁻⁶⁷, 7) Living with one biological parent, two biological parents, a stepparent, a relative, or other.^{68, 69}

4.2. Number of Participants

We proposed to recruit approximately 244 eligible cases that will be placed in 3 treatment arms: inpatient, in-person OCIC and telehealth CIS. We expect to recruit a small proportion of the suicidal adolescent group in the ED or who receive crisis assessment from telehealth or via phone. To test Aim 1, we will use Cox proportional regression model (CPR) to test whether the telehealth only CIS; outpatient, in-person CIS; and in-patient CIS groups have different incidence rates for recurrent episodes within 3 months. We expect that the sample sizes for the three arms will be *at least* 75, 75, and 70 respectively. To test Aims 2 and 3, we will use the generalized linear model (GLM) to evaluate whether telehealth only CIS; outpatient, in-person CIS; and in-patient CIS groups have different levels of changes in emotional arousal (Aim 2) and treatment satisfaction (Aim 3) at 3 months, after adjusting for several covariates (e.g., age, gender, triage “location”). For CPR, we will have power for our pilot study greater than 0.70 assuming a hazard ratio of 2.8 and greater than 0.8 for our GLM analyses assuming $f^2 = 0.1$ and correcting for multiple comparisons.

Recruitment Plan for Prospective Studies

. Estimated number of potentially eligible study participants	500
. Total number of study participants expected to be screened:	300
. Total number of study participants expected to be eligible of those screened:	270
. Target sample size (use same number stated in milestones):	244
. Total number of practices or centers that will enroll participants:	4
. Projected month first participant enrolled (month after project initiation):	2nd Month

• Projected month last participant enrolled (month after project initiation):	10 th Month
• Projected rate of enrollment (anticipated number enrolled per month of enrollment period):	2- 10/month
• Estimated percentage of participant dropout:	10%

4.3. End of Study Definition

The end of the study is defined as the date, October 1, 2021, or when the last participant completes the last study visit.

5. Study Population

The study population and the study settings are appropriate for the proposed research question as we will include adolescents (ages 12 to 18) who present in the ED or for crisis assessment with suicidal ideation and who have been recommended from treatment in one of the following treatment arms: inpatient, in-person OCIC, and telehealth CIS. After discussion with our patient/parent partners and site clinicians, we determined that the appropriate study population is patients presenting to the ED in a mental health crisis with a history of suicidal-related symptoms and behaviors who are clinically judged to require a mental intervention following the ER visit or crisis assessment that could be safely treated in inpatient care or intensive outpatient management, in-person or telehealth.

5.1. Workflow

The START Non-intervention study workflow is as follows:

- Patient presents in the ED or crisis assessment with chief complaint of suicidal ideation.
- Patients will be assessed by a mental health clinician and treatment will be determined. The CHRT-SR will be clinically obtained or during baseline data gathering at crisis assessment.
- If a patient is determined to need inpatient, in-person OCIC or telehealth CIS, they are eligible for the study and will be contacted by research staff to introduce the study.
- If patient and guardian agree to be in the study, they will be remotely consented and complete baseline surveys.
- Patient will be contacted every 2 weeks for up to 6 months to complete surveys.

Consistent with Informed Consent standard operating procedures a guardian can withdraw consent at any time in the study.

5.2. Informed Consent

To avoid causing undue stress and burden to patients and their families, research coordinators will use a script when gaining consent that is specifically designed to minimize burden and stress. Research coordinators will be provided with extensive formal training regarding the proper administration of the informed consent process. This will be documented in the Study Staff Checklist.

We will be obtaining documented consent for this study. Consent will be obtained either in person or through REDCap. Study personnel will initiate the e-consent process and explain the study and the e-consent/assent forms. Participants will have the opportunity to ask questions prior to deciding whether to continue with enrollment or to decline. All participants will have the capacity to provide e-consent.

For this study, the IRB approved consent/assent document has been uploaded into the REDCap database. The IRB approved document has been modified to an electronic format, but will include all of the same elements as the IRB approved document (i.e. IRB number, approval dates, and CCHMC logo, etc.). The electronic informed consent form includes fields for full name, signature, and date and time of the signature for the consenter and witness, along with text that states that all signatures are associated with the Subject ID# registered in the database. When completed, REDCap will generate a footer that contains the long date and time the document was submitted and “Confidential” listed in the header as an added precaution to preserve the research participants’ confidentiality.

The HIPAA Consent is queued to automatically open once the consent has been signed and all logic is satisfied.

For the HIPAA and Notice of Privacy Practices the IRB approved consent document will be uploaded into the database instrument. The instrument includes fields to capture full name, signature, and date and time of the signature for the consenter, and witness and conditional text that states that all signatures are associated with the Subject ID# registered in the database.

Signature process:

Participants and Witnesses will type their first and last name into a text box, sign their name in the signature field with a stylus or finger and then click “Now” by the date field to automatically enter the date and time. A copy will be printed or sent electronically to the subject per their preference.

5.3. Payment for Participation

Study participants (i.e. the adolescent patient) will be paid \$20 for each survey completion for up to 6 months for their time and effort. Payments will be given upon completion of each milestone survey. Participants will receive payment for this study in the form of a reloadable debit card (Clincard).

5.4. The CHRT-SR and Recruitment

The CHRT-SR will be obtained at baseline and at all follow up milestones. The baseline CHRT-SR will be used to help identify a consistent population group for analysis across all treatment

arms. The baseline CHRT-SR will be clinically obtained and can be accessed through the medical record or will be obtained during baseline data gathering. The distributions of CHRT-SR scores from the beginning months, November 2019 to March 2020, of the START study are shown in Figure 2. One-way ANOVA was used to evaluate whether the three disposition groups differ by CHRT-SR scores. The results suggest that CHRT-SR scores did not vary by the disposition outcome ($F = 0.23$, p -value = 0.7921, Barlett's test for equal variance $\chi^2 = 4.55$, p -value = 0.103). We further used multinomial logistic regression model to examine whether CHRT-SR scores could predict the disposition outcome, and results also indicate that the outcome was independent of the score ($p > 0.05$ for two comparisons: Bridge vs. Outpatient and Inpatient vs. Outpatient, separately).

[figure not shown]

Figure 2. CHRT-SR scores stratified by disposition status.

Participant's ability to understand and read English may be determined through screening questions during initial recruitment before the consenting process. If participants are able to understand English but have difficulty with reading, then questionnaires and surveys may be read to them.

5.5. Inclusion Criteria

Participants are eligible to be included in the study only if all of the following criteria apply:

1. Adolescents that are 12 through 18 years old.

2. Are brought to the Emergency Department (ED) or for crisis evaluation due to suicidal thoughts or behaviors
3. Require a higher level of care (In-person OCIC, Inpatient, or Telehealth CIS)
4. The presence of a legal guardian for consent
5. Capable of giving signed informed consent/assent, which includes compliance with the requirements and restrictions listed in the informed consent form (ICF) and in this protocol.

5.6. Exclusion Criteria

Participants are excluded from the study if any of the following criteria apply:

1. Adolescents with suicidal thoughts who had prior OCIC treatment in the past 12 months
2. Adolescents without the ability to answer survey questions
3. Adolescents that are non-English speaking due to the scales and surveys that are used for this study only being available in English.

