2.1. Study Rationale

The COVID-19 pandemic has led to disruptions throughout medicine, including psychiatry. The vast majority of psychiatric services at institutions across the country have rapidly shifted to telehealth-based services. This includes services for adolescents with suicidal ideation. Although this shift was done to provide services in a time of crisis that all but eliminated face-to-face services, the mental health community is left with questions regarding safety and effectiveness of telehealth. This is especially true for adolescents with suicidal thoughts. Previous research that explored the use of telehealth in mental health services has focused primarily on rural populations where services are limited (Roberts et al 2017, Saurman et al, 2014). Research has not specifically examined the effectiveness and safety of telehealth for adolescents with suicidal thoughts. This is partly attributable to restrictions on telehealth like state regulations, licensing, insurance, and equipment (Mace et al, 2018). However, the US response to COVID-19 has effectively eliminated these barriers. Currently, there is an unprecedented use of telehealth across US health systems. Yet, there is a deficiency of research indicating that telehealth for adolescents with suicidal thoughts is safe *and* effective. Given the current changes and their potential for long-term or permanent implementation, knowledge is urgently needed establish whether telehealth is a safe and effective approach for adolescents with suicidal thoughts. The START study is in a unique position to evaluate telehealth services relative to the current standards of care. By integrating an enhancement project into our current START study, we will be able to make a critical contribution to the learning of safe and effective treatment for adolescents experiencing suicidal thoughts now and in the future. The mental health community needs to determine the factors that can identify the safety of treating adolescents with suicidal thoughts in an outpatient and telehealth setting.

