Alternative Treatment to Standard Treatment of Adolescent Suicidality: Telehealth services encompass an emerging intervention due to the need for social distancing measures. They encompass crisis interventions that include safety planning, therapeutic interventions and emergency medication consultations. Telehealth services will not be the same at all sites, but involve similar services.

At CCHMC, our study team developed the term Outpatient Crisis Intervention Clinic (OCIC) to encompass the programs from the 4 individual sites, CCHMC, Northwell Health, Nationwide Children's and Children's Health, that provide similar, but not the same, services. The 4 programs that encompass the term OCIC have some variation in treatment approaches and duration, however all 4 programs have crisis intervention work in common, including appointments that occur soon after emergency department visits for crisis intervention. In comparison to inpatient psychiatry, Outpatient Crisis Intervention Clinic (OCIC) provides more intensive therapeutic services for adolescent suicidality with frequent family focused mental health appointments, specific therapeutic interventions for suicidality while outside of the hospital, and more thorough safety planning to prevent future suicidal events. OCIC has advantages because it provides a more intensive level of short-term (about two to six weeks) support with multiple therapeutic visits for adolescents with suicidality and their families each week starting within three days of the crises. OCIC provides these services for the adolescents and their families who are waiting for outpatient services without exposing these adolescents to the above-mentioned disadvantages

Gaps in Knowledge about Outcomes of Alternative Treatment of Adolescent Suicidality: Few programs have been developed that bridge the vulnerable period of time spanning between Emergency Room evaluation for adolescent suicidality to outpatient care,⁸⁸⁻⁹⁰ and even fewer that provide intensive treatment in an outpatient setting for teens.¹⁷ As such, there is tremendous need to develop and test optimal treatment strategies for adolescents during this high risk period, as highlighted in Objective 8.4 of the National Strategy for Suicide Prevention, to “promote continuity of care and the safety and well-being of all patients treated for suicide risk in emergency departments or hospital inpatient units.”⁹¹

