5.7. Screen Failures

Screen failures are defined as participants who consent to participate in the clinical study but are not subsequently included in the study. A minimal set of screen failure information is required to ensure transparent reporting of screen failure participants to meet the Consolidated Standards of Reporting Trials (CONSORT) publishing requirements and to respond to queries from regulatory authorities. Minimal information includes demography, screen failure details, eligibility criteria, and any serious adverse events (SAE).

Individuals who do not meet the criteria for participation in this study (screen failure) may be rescreened. Rescreened participants will be assigned the same participant number as for the initial screening.

6. Treatments

Study treatment is defined as psychiatric treatment within either Outpatient Crisis Intervention Clinic (OCIC), on an Inpatient unit, or telehealth crisis intervention services. Participants will be placed in the treatment setting by the assessing clinician. These therapeutic interventions are available whether or not the subject agrees to participate in the study.

Telehealth crisis intervention services (telehealth CIS) is defined as psychiatric services provided via telehealth services that is expected to be scheduled within 7 business days of the crisis assessment. Interventions can be with a social worker, therapist or psychiatrist. Services are not in person and occur over a computer video/phone system.

Inpatient treatment includes supportive individual therapy, improving patient's coping skills, family meetings about safety planning, and medication management.^{6-9, 81}

OCIC services include crisis psychotherapy/intervention, evidence-based screening/risk assessments, coordination of care/referral to an ongoing provider, short-term therapy/crisis treatment, safety planning, and/or referral and linkage to follow-up care. Treatment in OCIC may include group therapy, individual therapy, and/or family therapy, depending on the site. Please

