Evaluatable	Inclusion: 1) Adolescents (12 to 18 years old) who were brought to the ED due to suicidal thoughts or behaviors and require a higher level of care (Telehealth, OCIC or inpatient); 2) The presence of a legal guardian. Exclusion: 1) Adolescents with suicidal thoughts who had prior OCIC treatment in the past 12 months will be excluded; 2) Adolescents without the ability to answer survey questions will be excluded.
Safety	Participants will be analyzed according to the treatment they actually received.

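### The 12-month prior-treatment exclusion names only OCIC, so only the OCIC arm is free of recent repeat users of its own treatment, and no Aim 1 covariate records prior treatment

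*Combined protocol and SAP*

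**What the plan says.** Section 5.6 opens with "Participants are excluded from the study if any of the following criteria apply" and lists three exclusions. Only the first concerns earlier treatment: "Adolescents with suicidal thoughts who had prior OCIC treatment in the past 12 months". The Evaluatable row of the population table in section 9.1 carries it over: "Adolescents with suicidal thoughts who had prior OCIC treatment in the past 12 months will be excluded". Neither place mentions earlier telehealth CIS or earlier inpatient treatment, and no reason is given for singling out OCIC.

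Elsewhere the three settings are kept apart. Inclusion criterion 3 in section 5.5 reads "Require a higher level of care (In-person OCIC, Inpatient, or Telehealth CIS". Section 6 says of telehealth CIS: "Services are not in person and occur over a computer video/phone system". The label OCIC is itself loose, however. Section 2.2 says that "our study team developed the term Outpatient Crisis Intervention Clinic (OCIC) to encompass the programs from the 4 individual sites", which describes programs and not a mode of delivery. The inclusion criterion adds the word in-person; exclusion 1 does not.

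On assignment, section 6 states: "Participants will be placed in the treatment setting by the assessing clinician". On analysis, section 9.2.1 describes a Cox model of time to first suicidal event on treatment option and names no prior-treatment covariate.

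**The concern.** In a three-arm comparison without randomisation, the eligibility rules help decide who sits in each arm. Here the rule screens on the history of one arm's treatment only. A patient who finished OCIC 11 months ago is out. A patient who left an inpatient unit, or finished telehealth CIS, three weeks ago and is again in crisis is eligible.

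Recent treatment may mark a different level of risk. Section 2.2 describes the first month after inpatient discharge as the time of greatest reattempt risk, and in the Dallas data it associates later attempts and events with more previous attempts. If the arms hold different shares of recently treated patients, the Aim 1 hazard ratio mixes that difference with the effect of setting. The telehealth-versus-OCIC contrast has little room for this: section 9.1 expects a hazard ratio below 2 there, with power likely below 0.6.

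**Working it through.** The plan gives no figure for this point, so there is none to reproduce. The check is of the text first, then of the possible size under stated assumptions.

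**Step 1. Who can enter which arm.** Applying section 5.6 as written:

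| Earlier treatment | OCIC arm | Telehealth arm | Inpatient arm |
|---|---|---|---|
| OCIC, within 12 months | excluded | excluded | excluded |
| Telehealth CIS, within 12 months | eligible* | eligible* | eligible* |
| Inpatient, within 12 months | eligible | eligible | eligible |
| OCIC, more than 12 months ago | eligible | eligible | eligible |

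*Unless a site counts its OCIC program delivered by telehealth as prior OCIC. The text does not settle this.

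The asymmetry lies in the own-treatment cells: OCIC in the OCIC arm is excluded, while telehealth in the telehealth arm and inpatient in the inpatient arm are eligible. The other cells do not differ between arms.

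**Step 2. Does anything planned correct it?**

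- Primary Cox model (9.2.1): treatment option only.
- Covariates for Aims 2 and 3 (4.2 and 9.2.3): given as examples, namely age, gender and triage location.
- COVID-19 survey indicators (9.2.3): to be used as covariates under Aims 1 to 3; they describe mood, stress and well-being.
- Number of suicidal events at baseline (9.2.3): listed for heterogeneity of treatment effect, not for adjustment. The event definition in 2.2 includes hospitalisation for suicidal risk, so it may pick up some earlier admissions. It does not pick up a course of telehealth CIS.
- CHRT-SR (5.4 and 8): measures severity of ideation, not treatment history.
- Demographic list (4.1) and Schedule of Events (11.1): no prior-treatment item is named.

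None of these captures prior treatment across the settings.

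**Step 3. Possible size.** Let q be the share of an arm with any recent crisis or inpatient treatment, and r the hazard of such patients relative to the rest. With no true treatment effect, the approximate telehealth-to-OCIC hazard ratio is

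ratio = (1 + qT(r − 1)) / (1 + qO(r − 1)).

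The documents give neither q nor r. Assume q from 0 to 0.25 in each arm and r from 1.5 to 3:

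- qT = 0.10, qO = 0, r = 1.5: 1.05 / 1 = 1.05
- qT = 0.25, qO = 0, r = 3: 1.50 / 1 = 1.50
- qT = qO, any r: 1.00
- qT = 0.10, qO = 0.20, r = 2: 1.10 / 1.20 = 0.92
- qT = 0, qO = 0.25, r = 3: 1 / 1.50 = 0.67

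Setting qO to 0 would need an OCIC arm without recently treated patients of any kind. The table in step 1 shows that the rule does not produce that. The same formula applies to inpatient versus OCIC.

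**Step 4. Can document figures stand in for q?** No. The 27.3% in section 2.2 is suicidal events within 6 months among 286 Dallas respondents, and the 19% in section 9.1 is a six-month readmission rate from a cited cohort. Both describe follow-up after treatment, not the share of new enrolments with recent treatment.

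**The case against.** The strongest reply is that the rule is milder than it looks. It applies to the whole study, so recent OCIC users leave every arm. Its look-back is only 12 months. OCIC is an umbrella term, so a site could read it to include remote delivery. Section 2.2 says telehealth CIS has only lately come into wide use, so earlier users may be few at the start of enrolment. Baseline CHRT-SR is meant to identify a consistent population, baseline events are collected, and section 9.2 promises a fuller analysis plan on participant selection before database lock.

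Much of this stands, and it rules out two stronger readings. A reader might infer that the OCIC arm holds only first-time users. It does not: OCIC treatment more than 12 months earlier is allowed, and so is recent inpatient or telehealth treatment. A reader might also infer a tilt towards finding telehealth harmful, the direction SA1 hypothesises, especially since section 2.1 says "Although this shift was done to provide services in a time of crisis that all but eliminated face-to-face services". That needs repeat users to return to the same setting, which no section supports. Sections 7 and 8.2.2 describe worsening telehealth or OCIC patients going to ED evaluation, partial hospitalisation or inpatient care, which would move some out of the telehealth arm. The remark in section 2.1 does not give the share of look-back care that was telehealth CIS.

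The reply does not restore symmetry. Scarcity of earlier telehealth users says nothing about inpatient treatment, and telehealth courses are short (one to three visits up to 4-6 weeks) against enrolment running from month 2 to month 10, so earlier users can accumulate. The ambiguity in the term OCIC means four sites may apply the exclusion differently.

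**Conclusion.** The one-sided look-back is in the text of sections 5.6 and 9.1, is unexplained, and is not corrected by any covariate named for Aim 1. With setting chosen by clinicians, the arms can differ in recent treatment history. The documents do not support a claim about the direction or size of the resulting bias. The 0.67 to 1.50 range rests wholly on the assumed shares and relative hazards and includes no bias at all. The conclusion that prior telehealth CIS is unrestricted rests on the natural reading that OCIC and telehealth CIS are separate; the inpatient part needs no such reading. The point is worth acting on because the information is inexpensive to collect at baseline.

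**What to change.** 1. In section 5.6 and the Evaluatable row of section 9.1, state whether OCIC includes a site's program delivered by telehealth.
2. Record at baseline any OCIC, telehealth CIS or psychiatric inpatient treatment in the past 12 months, with the setting. Section 4.1 already plans EHR review for the baseline forms within 72 hours of admission.
3. Include a single yes/no indicator of any such treatment in the Aim 1 Cox model, or repeat the Aim 1 comparison in patients with none. An indicator of earlier treatment in the same setting would not serve, because exclusion 1 removes such recent users from the OCIC arm. The restricted comparison applies one look-back to all arms.

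The cost is one baseline field and one covariate or sensitivity analysis, with less precision in the restricted set. No participants are lost.

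Adding telehealth CIS to the exclusion is a weaker option. It leaves the inpatient asymmetry in place. If 10-25% of a 75-patient telehealth arm were recent users (an assumption), it would remove about 8 to 19 patients (7.5 to 18.75), against a margin of 270 − 244 = 26 between those expected to be eligible and the target in section 4.2.
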